10.1.1 Device Related Adverse Event (AE)

Any untoward medical occurrence, unintended disease or injury or any untoward clinical signs (including an abnormal laboratory finding) in subjects, users or other persons occurring as a result of the study device

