4. INTRODUCTION

4.1 Background

Hemodynamic optimization of critically ill patients is a goal for clinicians in order to afford the patient the best possible outcomes. Being able to precisely and rapidly determine patient fluid responsiveness provides the bedside physician and nursing staff the information needed to make critical decisions in regards to the patient's fluid status and management of additional fluids and medications. Patient management in the ICU is complex and multiple studies and meta-analyses have shown that clinicians struggle to diagnose which patients will benefit from fluid administration (i.e. the administration of intravenous fluids will increase cardiac output).¹ The findings show that up to 50% of patients in the ICU will not benefit from fluid administration.² Studies have also shown that excessive fluid administration and fluid retention leads to poorer outcomes.³⁻⁵ Well-timed decision making with accurate information is critical and challenging particularly in the setting of a patient with sepsis.

As fluid management and cardiac output determination are linked to better decision-making and improved outcomes in ICU, the use of a dynamic assessment of fluid responsiveness becomes a key tool for patient management. The Noninvasive Starling SV device, which is FDA cleared and CE marked, is currently in clinical use and can be used to provide a dynamic assessment of fluid responsiveness. This study will show the clinical utility of initiating an assessment of patient fluid responsiveness prior to the administration of treatment fluid.

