10.1.2 Serious Adverse Events

A serious adverse event (SAE) is any untoward medical occurrence that:

- Results in death
- Led to serious deterioration in the health of the subject, that either resulted in:
 - a life-threatening illness or injury, or
 - a permanent impairment of a body structure or a body function, or
 - in-patient or prolonged hospitalization, or
 - medical or surgical intervention to prevent life-threatening illness or injury or permanent impairment to a body structure or a body function,
- Led to fetal distress, fetal death or a congenital abnormality or birth defect

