10.2 Reporting Procedures

10.2.1 General Reporting Requirements

All device related adverse events must be recorded on the Adverse Event eCRF by the investigator (or designee). The report should include: start date of the adverse event, treatment,

resolution, and assessment of both the seriousness and the relationship to the investigational device.

The following criteria must also be adhered to by the Investigator:

- Completion of separate device related Adverse Event forms to document each event
- The forms must be signed by the Investigator, and
- Supplying to the Sponsor (or designee), upon Sponsor's request, with any additional information related to the safety reporting of a particular event

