13.5 Data Retention

Study documents should be retained for a minimum of 5 years. These documents should be retained for a longer period, however, if required by local regulations. No records will be destroyed without the written consent of the Sponsor, if applicable. It is the responsibility of the Sponsor to inform the Investigator when these documents no longer need to be retained.

Table 2: Responsibilities for Preparing and Submitting Reports

Type of Report	Prepared by Investigator for	Time of Notification
Enrollment Notification Form	Sponsor	Within 24 hours of procedure
Electronic Case Report Forms	Sponsor	Within 10 working days
Serious/ Device Related Adverse Event	Sponsor and IRB (as required)	Within 24 hours of knowledge or as required by IRB
Subject Death	Sponsor and IRB (as required)	Within 24 hours of knowledge
Subject Withdrawal	Sponsor	Within 24 hours of knowledge
Withdrawal of IRB Approval	Sponsor	Within 24 hours of knowledge
Protocol Deviations	Sponsor and IRB	Within 5 working days of occurrence or knowledge
Informed Consent Not Obtained	Sponsor and IRB	Within 24 hours of knowledge or as required by IRB
Final summary report	Sponsor and IRB and Regulatory Authority (as required)	Within 3 months of study completion

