### 9.2.2 NOT FOR FORMAL TESTING

#### 9.2.2.1 Incidence of Treatment Emergent Adverse Events (AE)

A Treatment Emergent Adverse Event (TEAE) is one that started or worsened in severity during or after randomized treatment was attempted. The number and percentage of patients with incidence of at least one TEAE will be summarized by treatment arm in a table. The summary will include the number and percent of subjects experiencing one or more AEs cumulatively up to 72 hours, one week, and 30 days. Though no formal hypothesis tests are planned, 95% confidence intervals for the difference in rates between the two arms at each time point will be completed and included using the normal approximation to the binomial distribution.

The analysis will be repeated for serious TEAS. In addition, the number and percentage of patients with at least one TEAEs will be presented by severity and relationship to study procedure; patients with more than one TEAE will be categorized according to the maximum severity and maximum relationship experienced.

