### 10.1 ALL TREATMENT EMERGENT ADVERSE EVENTS

The number of TEAEs and the number and percentage of patients with at least one TEAE, with at least one device-related TEAE, with at least one serious TEAE and with at least one device-related TEAE will be presented by treatment group. These summaries will be presented for TEAEs occurring from start of treatment through 72 hours, from 72 hours through Discharge, from Discharge through 30 days, and from the start of treatment through 30 days.

The number of TEAEs and the number and percentage of patients with at least one TEAE will be presented for each treatment group by MedDRA system organ class and preferred term. This analysis will be repeated for serious TEAEs (collected through 72 hours only), device-related TEAEs, and AEs leading to withdrawal from the study.

In addition, the by-treatment number and percentage of patients with at least one TEAEs will be presented by severity and relationship to study procedure within each system organ class and preferred term; patients with more than one TEAE within a given system organ class and preferred term will be categorized according to the maximum severity and maximum relationship experienced.

A listing of all adverse events will include the subject number, AE number, days since index procedure, the AE SOC and PT, the severity of AE, whether the AE is classified as serious (SAE), the relationship of the AE to the investigational device or procedure, the action taken, the outcome, and the adjudication status.

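### The SAP compares all-cause adverse event incidence between arms, but the protocol requires non-serious events to be recorded only when they are device-related

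*Protocol*

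**What the plan says.** **What the protocol collects.** Section 10.1 and its subsections define two classes of event.

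- A device-related AE (10.1.1) must arise "in subjects, users or other persons occurring as a result of the study device". Section 10.2.1 requires these to be entered on the AE form, with an "assessment of both the seriousness and the relationship to the investigational device".
- For the serious class (10.1.2), "A serious adverse event (SAE) is any untoward medical occurrence that" meets one of the listed outcomes. No device link is needed and the definition does not depend on arm. Section 10.2.2 requires all SAEs to be reported; 10.1 says they are collected in five organ areas.

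The reporting table in Protocol 13.5 (Table 2) has one line for such events, "Serious/ Device Related Adverse Event". No section requires a non-serious event that is not device-related to be recorded.

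**What the SAP analyses.** Section 9.2.2.1 defines a TEAE by timing or worsening alone, with no causal condition. It summarises the percentage of subjects with at least one TEAE by arm and adds that "95% confidence intervals for the difference in rates between the two arms at each time point will be completed". It then repeats the analysis for serious events. Section 10.1 counts all TEAEs and device-related TEAEs as separate lines, so it treats the second as a subset of a wider total. It also asks for TEAEs "presented by severity and relationship to study procedure within each system organ class and preferred term".

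**Who wears the device.** Protocol 8.1, 9.2 and Table 1 describe sensor placement on eligible subjects without naming an arm. The mITT definition (Protocol 12.2.3) requires monitoring only in the treatment group.

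**The concern.** The SAP's total assumes that non-serious events of every cause reach the database; under the protocol they need not. The arms differ in how fluid is given, and the protocol's own rationale is that "excessive fluid administration and fluid retention leads to poorer outcomes". A non-serious complication of too much fluid in a control subject, or of too little in a guided subject, need not be recorded as an AE unless someone attributes it to the device.

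Two things are at stake. First, a table headed as any TEAE would be read as an all-cause safety comparison that the data cannot support. Second, if controls are not exposed to the device, part of the difference between arms would come from the recording rule itself.

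**Working it through.** The documents give no AE rate, margin or power, so there is no figure of the plan's to reproduce. The check is a comparison of sections, followed by an illustration.

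**Step 1. Collection against analysis**

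| Event | Must the protocol record it? | Does the SAP count it as a TEAE? |
|---|---|---|
| Serious, any cause | Yes (10.1.2, 10.2.2; five areas in 10.1) | Yes |
| Non-serious, device-related | Yes (10.1.1, 10.2.1, Table 2) | Yes |
| Non-serious, not device-related | No section requires it | Yes |

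The third row is the gap. Protocol 12.2.1 says AEs will be reported for all enrolled subjects, but that sets the population and does not widen the definition in 10.1.1.

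**Step 2. Size of the artefact if controls do not wear the device**

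Let s be the SAE proportion, equal in both arms, and p the proportion of Starling subjects with a device-related non-serious AE. Both are assumptions: s = 10–30% and p = 2–10%, the latter kept low because Protocol 10.1 expects few device-related events. Assuming independence:

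- Starling rate = 1 − (1 − s)(1 − p)
- Control rate = s
- Difference = (1 − s)p

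The half-width uses the SAP section 5 arm sizes of 80 and 40: 1.96 × √[T(1 − T)/80 + s(1 − s)/40], where T is the Starling rate.

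| s | p | Starling | Control | Difference (points) | 95% half-width (points) |
|---|---|---|---|---|---|
| 10% | 2% | 11.8% | 10% | +1.8 | 11.7 |
| 10% | 10% | 19.0% | 10% | +9.0 | 12.7 |
| 30% | 2% | 31.4% | 30% | +1.4 | 17.5 |
| 30% | 10% | 37.0% | 30% | +7.0 | 17.7 |

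The artefact is +1.4 to +9.0 points and the half-width about 12 to 18 points. At the maximum of 210 (140 v 70 at 2:1) the half-widths shrink by √(120/210) = 0.756. The closest case becomes 9.0 against 12.66 × 0.756 = 9.6, still inside the interval.

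**Step 3. If both arms wear the device**

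The same rule then applies to both arms. With equal device-related rates the expected difference is zero, but the rate is still SAEs plus device-related events.

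**Step 4. What goes unrecorded on either reading**

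Suppose, for illustration, that the true proportions with a non-serious AE of any cause were 30% and 45%. The true gap in any AE would be (1 − s) × 15 points: 13.5 points at s = 10% and 10.5 points at s = 30%. None of it need appear in the data except where an event was judged device-related.

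**The case against.** **Harm is captured elsewhere.** SAEs are defined by outcome whatever the cause. Creatinine, RRT, ventilation, MACE and mortality are all summarised by arm, and Protocol 9.3.3 records significant clinical events such as arrest and intubation. This stands. A reader might infer that harm from the fluid strategies is left out altogether; the documents do not support that. Only non-serious harm is missed. Nor does the background section name non-serious overload: it speaks of worse outcomes, which those endpoints measure.

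**Controls probably wear the sensors.** Protocol 8.1, 9.2 and Table 1 name no arm, and 7.2 seeks subjects to whom the system can be attached. A reader might infer that the two arms' rates necessarily measure different things, or that a control subject can never have a non-serious AE. That follows only if controls are unexposed. The mITT wording leaves this open without establishing it.

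**The artefact is small beside the interval.** This stands at plausible device-event rates. A difference as large as the half-width needs p near 20% (16.0 points against 16.3 at s = 20%), which sits badly with the protocol's expectation of few such events.

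**The case report form may hold more fields.** The SAP was written against forms issued in December 2017 that are not among the documents. Protocol 10.2.1 does not list severity either, yet the SAP tabulates it. It is therefore not shown that the table of relationship to study procedure lacks a source, only that the protocol text does not provide one.

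**The comparison is descriptive.** It lies outside formal testing and no success claim depends on it. That limits the weight of the point but does not make the label correct.

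**Conclusion.** The point holds in a limited form. The SAP's any-TEAE incidence cannot be built from what the protocol requires to be recorded; what would be reported is the incidence of serious or device-related events. Non-serious harm from either fluid strategy is outside it. That conclusion rests on the text alone and does not depend on who wears the device, although the unseen forms could collect more than the protocol demands.

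Bias between arms is conditional. If controls do not wear the device, the assumed rates give about +1.4 to +9 points against Starling with no true difference, within the CI half-width of about 12–18 points at 80 v 40. If both arms wear it and device-related rates are equal, the expected artefact is about zero. AE incidence is a listed secondary endpoint, so the table should be corrected, but the primary and formally tested analyses are unaffected.

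**What to change.** In SAP 9.2.2.1 and 10.1:

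1. Drop the between-arm difference and CI for any TEAE and give them for SAEs only. These are defined alike in both arms, and 9.2.2.1 already plans that analysis. First reconcile the five SAE areas in Protocol 10.1 with the duty in 10.2.2 to report all SAEs.
2. State whether control subjects wear the device. Report device-related AEs as a rate among device-exposed subjects, with no between-arm CI unless both arms wear it.
3. Label the combined tables as serious or device-related events.
4. Check the case report form for a field on relationship to study procedure, and drop that table if there is none.

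The table changes are SAP wording and need no new data; the SAE reconciliation and the statement on device exposure may also need the protocol text clarified. The cost is that no overall AE difference is reported. Non-serious harm unrelated to the device also stays uncollected, and the study report should state this as a limitation.

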10.1.2 Serious Adverse Events

A serious adverse event (SAE) is any untoward medical occurrence that:

- Results in death
- Led to serious deterioration in the health of the subject, that either resulted in:
 - a life-threatening illness or injury, or
 - a permanent impairment of a body structure or a body function, or
 - in-patient or prolonged hospitalization, or
 - medical or surgical intervention to prevent life-threatening illness or injury or permanent impairment to a body structure or a body function,
- Led to fetal distress, fetal death or a congenital abnormality or birth defect

10.2 Reporting Procedures

10.2.1 General Reporting Requirements

All device related adverse events must be recorded on the Adverse Event eCRF by the investigator (or designee). The report should include: start date of the adverse event, treatment,

resolution, and assessment of both the seriousness and the relationship to the investigational device.

The following criteria must also be adhered to by the Investigator:

- Completion of separate device related Adverse Event forms to document each event
- The forms must be signed by the Investigator, and
- Supplying to the Sponsor (or designee), upon Sponsor's request, with any additional information related to the safety reporting of a particular event

10.2.2 Reporting Requirements of SAEs

All serious adverse events must be reported by the investigator by submitting the Adverse Event eCRF within 24 hours of learning of the adverse event.

The Investigator shall:

- a) Report to the IRB serious adverse events per the institutional requirements for timing and amount of support information,
- b) Supply the Sponsor (or designee), upon Sponsor's request, with any additional information related to the safety reporting of a particular event.

10.2.3 Sponsor Reporting

All adverse events will be reported to the applicable regulatory authority as required per applicable regulatory authority.

Cheetah Medical, or their designee is responsible for the classification and reporting of adverse events and applicable regulatory requirements.

11. STUDY MONITORING

The study will be monitored according to Cheetah Medical's monitoring procedures. A study specific monitoring plan will be developed to ensure protocol compliance and applicable regulatory requirements.

Clinical monitors will be designated by Cheetah Medical. Monitors will verify subject data and ensure compliance with GCP, clinical protocol and other study requirements to be utilized for the study.

11.1 Monitor Training

All Cheetah Medical designated monitors will be trained appropriately to monitor study progress including but not limited to the protocol and CRFs.

11.2 Site/Investigator Training

Cheetah Medical will be responsible for providing training to the investigator and appropriate clinical site personnel.

11.2.1 Protocol Training

Training on study protocol requirements will be provided for the entire study team at the initiation of the study. It is ultimately the responsibility of the Investigator to ensure all clinical site personnel participating in this study are adequately trained.

To ensure uniform data collection and protocol compliance, Cheetah Medical and/or designee will perform study initiation visits to review the clinical protocol, techniques for the identification of eligible subjects, instructions on in-hospital data collection, and methods for soliciting data from alternative sources.

11.2.2 Device Training

This procedure may only be performed by qualified investigators, familiar with the Cheetah Medical system. Training on the Starling SV system will be performed and documented for the site Investigator who is responsible for using the device, by the study Sponsor, Cheetah Medical.

11.3 Site Monitoring

The Sponsor or designee may conduct periodic compliance assessments at various study sites. The Sponsor or designee may request access to all study records including source documentation for inspection and photocopying during a compliance assessment. The Investigator and research coordinator must be available to respond to reasonable requests and queries made during the compliance assessment process.

11.4 Regulatory Agency Inspection

In the event that an investigator is contacted by a regulatory agency regarding this study, the investigator will notify the Sponsor or its designee immediately. The investigator and research coordinator must be available to respond to reasonable requests and queries made during the inspection process. The investigator must provide the Sponsor or designee with copies of all correspondence that may affect review of the current trial. The Sponsor may provide needed assistance in responding to regulatory audits.

12. STATISTICAL CONSIDERATIONS

12.1 Sample Size Estimation

Subjects will be randomly assigned in a 2:1 ratio to treatment with Starling SV or to treatment with standard of care. The primary effectiveness endpoint for this study is the difference between the two treatment groups in mean fluid balance at ICU discharge.

Minimum enrollment (N_{\min}) in the study will be set at 120 subjects (80 Starling SV and 40 control) to power at 80% for possible demonstration of superiority for the secondary endpoint of creatinine levels as a measurement of change from baseline. The secondary endpoint for change in creatinine levels at 120 evaluable subjects displays 80% power at a two-sided alpha level of

0.05 to demonstrate superiority under an assumption of a treatment effect of -1.4 mg/dL with a standard deviation of 2.5 mg/dL.

Under an assumption of a treatment effect of -2 L with a standard deviation of 3 L, the sample size of 120 evaluable subjects provides 92.7% power in a test of superiority for the primary effectiveness endpoint.

The trial will incorporate a sample size re-estimation (SSR) at the time of the interim look based on promise for superiority in the key secondary endpoint. Methods for the SSR have been described in detail in previous literature. The maximum enrollment being considered for this trial is 210 total enrolled ($N_{\max} = 1.75 \text{ times } N_{\min}$).

An interim analysis incorporating a SSR will take place when 120 subjects have been enrolled and completed endpoint evaluations. The interim analysis will be performed by an independent statistician. It is assumed that the acute endpoint assessments will be fully informed at the time of the interim analysis.

At this point, the primary study endpoint will be tested as final, and will not incorporate an alpha spend.

The conditional power to claim superiority (CP_{sup}) on the key secondary endpoint for change in creatinine levels will be computed. The conditional power (CP_{sup}) will be calculated based on the interim results of the key secondary endpoint, with the specific interest of demonstrating superiority. CP_{sup} is defined as the approach that quantifies the statistical power to yield an answer different from that seen at the interim analysis. The data will be partitioned into three zones based on CP_{sup} unfavorable zone ($CP_{\text{sup}} < 50\%$), promising zone ($50\% \leq CP_{\text{sup}} < 80\%$), and favorable zone ($CP_{\text{sup}} \geq 80\%$).

12.2 Analysis Populations

12.2.1 All Enrolled

Any subject who has signed informed consent will be included in the all enrolled population. Should a subject be considered a screen failure, the reason for failure will be documented, and the subject will be exited from the study. Adverse events will be reported for all enrolled subjects through the time of study exit.

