8. SUBJECT POPULATION AND SELECTION

8.1 Subject Population

[figure not shown]
Adult subjects with the diagnosis of sepsis and refractory hypotension will be considered as a candidate for the study. A maximum of 210 subjects enrolled and in the analysis population will be included in the study. Subjects will be considered to be enrolled when they or their designated representative sign the informed consent form (ICF).

Subjects who are enrolled will be assigned a subject ID. Subjects that sign the ICF, but are found ineligible will be considered screen failures and will be exited from the study at that time. Enrolled subjects who meet study eligibility will be included in the analysis populations and are further described in **Section 12**.

The diagnosis of sepsis is defined as a known or presumed infection and the presence of 2 or more SIRS criteria as detailed in **Section 8.2**. Refractory hypotension is defined as the presence of hypotension following initial resuscitation with 1L of fluid. After obtaining ICF and confirming that the inclusion and exclusion criteria are met, the Cheetah sensors will be placed and connected to the Starling SV monitor. Useable readings will be confirmed prior to initiating the study data collection period.

A diagram outlining the overall subject enrollment plan is shown below:

Figure 1: Subject Flow Diagram

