8.7 Subject Discontinuation/Withdrawal Criteria

Once the subject has been enrolled in the study, she/he may withdraw her/his consent to participate in the study at any time without prejudice. Participation in this clinical investigation is entirely voluntary. Likewise, there may be a reason identified by the Investigator that deems the subject no longer suitable for the study. In either case, the Investigator will contact Cheetah Medical to discuss the circumstances for discontinuation/withdrawal. Discontinuation or withdrawal may occur for any of the reasons listed below (this list is not all inclusive).

1. Subject is uncooperative with compliance of required study tests and/or medical management
2. Investigator determines that subject has developed a condition in which continued participation in the study is considered potentially harmful to the subject
3. Subject withdraws their consent
4. Adverse event which is considered intolerable by the patient, their LAR or the Principal Investigator
5. Subject has a significant protocol violation
6. Subject incorrectly enrolled in the study
7. Cheetah Medical terminates the study

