8.7.1 Subjects Lost to Follow-Up

Subjects may be considered lost to follow-up for the following reasons:

- During data analysis, data indicates there is unacceptable bias in the measurements
- Data collection is interrupted prior to 72 hour data collection period of ICU stay
- Severe agitation and/or cardiopulmonary resuscitations resulted in poor quality data

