9.2 Enrollment Procedure

Assuming the subject meets all study eligibility criteria, the investigator, or designees, will place the Cheetah device (Starling SV) on the subject. The device will be evaluated for obtaining the optimum expected hemodynamic readings before the study is begun according to the Starling SV Instructions for Use (IFU). This is done to confirm that data collected from the monitoring devices will be evaluable. It is recommended that approximately 15-20 minutes are allowed for the device to autocalibrate and achieve a stable baseline prior to beginning any measurements at the initiation of the study.

If the Starling SV does not provide the expected hemodynamic recordings, it will be adjusted or replaced as needed until it provides the expected recordings. If it is determined that the device will not provide the expected recording, then the subject will be withdrawn from the study.

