10. SAFETY/DEVICE ASSESSMENT

10.1 Adverse Events

Subjects will be carefully monitored during the study for possible device related adverse events (AEs). The investigator or designee will determine AE occurrences and collect the required data. It is anticipated that the occurrence of device related adverse events will be a low number. All device related adverse events will be reviewed not only by the site investigator, but also by the sponsor's medical officer.

Serious Adverse events will be collected during the 72 hour (+ 48 hours) treatment period in the following areas: Cardiac, CNS, pulmonary, renal, and skin disorders.

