17. TERMINATION OF STUDY OR STUDY SITE PARTICIPATION

The Sponsor may terminate the study at any time. If the study is terminated prior to the completion of expected enrollment for any reason, all participating centers will be notified within five working days. All subjects already enrolled will continue to be followed for the planned course of study described in this protocol. The study shall be terminated following the last enrolled subject.

The Sponsor reserves the right to terminate study site participation and remove appropriate study materials at any time. Specific instances that may precipitate such termination include but are not limited to the following:

- Failure to meet minimum subject enrollment requirements
- Failure to comply with protocol specified procedures and documentation
- Failure to comply with regulatory regulations
- Failure to comply with Good Clinical Practice

The site Investigator may also discontinue study participation with suitable written notice to the Sponsor.

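### Stopping the device or algorithm is not separated from leaving the study, so serious adverse events after an early stop can be lost from the Safety analysis

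*Protocol*

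**What the plan says.** **End of reporting.** Protocol 12.2.1: "Adverse events will be reported for all enrolled subjects through the time of study exit". The term study exit is not defined.

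**Routes to exit.** Protocol 8.7 handles discontinuation and withdrawal as a single outcome and is permissive: "Discontinuation or withdrawal may occur for any of the reasons listed below". Reason 4 is: "Adverse event which is considered intolerable by the patient, their LAR or the Principal Investigator". Other reasons include a condition that makes continued participation potentially harmful, a significant protocol violation and incorrect enrolment. Under 8.7.1 a subject may be counted as lost to follow-up when "Data collection is interrupted prior to 72 hour data collection period of ICU stay", or when severe agitation or CPR has spoiled the data. Protocol 9.2 adds a start-up rule: "If it is determined that the device will not provide the expected recording, then the subject will be withdrawn from the study".

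**Collection window.** Protocol 10.1: "Serious Adverse events will be collected during the 72 hour (+ 48 hours) treatment period", in five organ areas. SAP 9.2.2.1 plans summaries at 72 hours, one week and 30 days. SAP 10.1 also plans summaries to 30 days, but describes serious events as collected to 72 hours only.

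**Follow-up after a stop.** Protocol 17, on early termination of the whole study: "All subjects already enrolled will continue to be followed for the planned course of study described in this protocol". Section 14.2 makes a similar promise for patients at a terminated site. There is no counterpart for an individual patient who is stopped.

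**SAP Safety set (6.5).** ITT subjects in whom study treatment was at least attempted, with no requirement that monitoring be completed.

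**The concern.** A patient who stops the intervention because of harm is one whose later course matters most to the safety comparison. If that stop can be recorded as study exit, and reporting ends at exit, observation ends when the risk may be highest. Section 8.7.1 goes further: a resuscitation, which is itself a serious event, can lead to the patient being classed as lost.

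The decision rests with investigators who know the assigned arm, so the same clinical event may end follow-up at one site and not at another. At stake are the adverse event and serious adverse event comparisons in the Safety set, and complete outcome data for any later ITT analysis.

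**Working it through.** The plan gives no figure on this point to reproduce. The check is a comparison of sections, followed by an illustration on stated assumptions.

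**1. Does any text keep an exited patient under safety observation?**
- Protocol 8.7: no. Its reason 7 is termination of the study by the sponsor, and section 17 keeps those patients in follow-up. So the protocol can separate stopping from leaving, but does so explicitly only for study and site termination.
- Protocol 13.1 and Table 2: the condition at withdrawal is to be documented and the sponsor notified. Serious events and deaths are reportable within 24 hours of knowledge, which does not create a duty to look for them after exit.
- SAP 6.5: changes who is in the denominator, not how long they are observed.
- SAP 9.2.2.1 and 10.1: set summary times, without saying that exited patients are followed to them.
- SAP 7.3: no imputation; the conditional sensitivity analysis covers the primary endpoint only.

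**2. Can a stopped patient also drop out of the Safety set?** Safety requires ITT membership (SAP 6.5), and ITT requires that eligibility criteria be met (SAP 6.2). Exclusion criterion 26 is uncoupling from the treatment algorithm, which can only happen after treatment starts. Read literally, it can remove such a patient. SAP 10 also reports adverse events on mITT, which requires completed monitoring in the Starling arm only (SAP 6.3).

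**3. Window at risk.** 72 + 48 = 120 h. Exit at 24 h leaves 120 - 24 = 96 h (80%) unobserved; exit at 48 h leaves 72 h (60%).

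**4. Illustration.** Let w be the share of an arm exited early and q the chance that an exited patient has a first event after exit. Exited patients stay in the denominator, as SAP 6.5 implies, and q is the same in both arms.
- Observed risk = p - w × q, where p is the true risk.
- Bias in the Starling-minus-control risk difference = -(w_T - w_C) × q.
- Starling patients whose event is missed = n_T × w_T × q.

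Assumed, not from the documents: w_T = 0.05 to 0.15 and q = 0.3 to 0.5. From the documents: n_T = 80 at N = 120, and n_T = 210 × 2/3 = 140 at the maximum.

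| Control exits | Bias, low end | Bias, high end |
|---|---|---|
| None | -0.05 × 0.3 = -1.5 points | -0.15 × 0.5 = -7.5 points |
| Half the Starling rate | -0.025 × 0.3 = -0.75 points | -0.075 × 0.5 = -3.75 points |
| Same as Starling | 0 | 0 |

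Missed in the Starling arm: 80 × 0.05 × 0.3 = 1.2 to 80 × 0.15 × 0.5 = 6.0 patients; with 140, 2.1 to 10.5. These losses occur even when the bias between arms is 0.

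**The case against.** The strongest reply has five parts.

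- **Exit is discretionary.** Section 8.7 says it may occur, and the synopsis has outcome data collected to hospital discharge. This stands against reading the plan as saying that a stop for an adverse event always means leaving the study. It does not close the gap: the synopsis gives the general schedule and does not say that it applies after withdrawal.
- **The 12.2.1 sentence follows one on screen failures, and SAP 6.5 changes it.** The sentence nevertheless covers all enrolled subjects, and the SAP changes the population without replacing the end point.
- **The event that prompts exit is captured.** Protocol 10.2.1 asks for resolution of device-related events, Table 2 asks for deaths, and SAP 10.1 tabulates events leading to withdrawal. This stands and limits the loss to what follows. A patient exited for a serious event within the collected areas already counts in the proportion with at least one; q therefore refers to first events after exit.
- **Arm imbalance is unproven.** A reader might infer that the loss falls mainly on the Starling arm and flatters it. Only that arm has an algorithm (Protocol 7.2) and a monitoring condition for mITT and PP, so imbalance is plausible. But the reasons in 8.7 and 8.7.1 apply to both arms. The signal rule in 9.2 is a start-up check that names no arm and may precede randomization; Protocol 8.1 says only that "the Cheetah sensors will be placed and connected to the Starling SV monitor". It should not be used as evidence of imbalance.
- **Efficacy results would not change.** A reader might expect this repair to remove bias from RRT, ventilation and mortality. If these are analysed as SAP 9 directs, on PP and mITT, Starling patients without completed monitoring are already removed by definition (SAP 6.3, 6.4). This objection stands in full.

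**Conclusion.** The gap is real and should be closed. Nothing in either document keeps a randomized patient in safety follow-up once the device, algorithm or recording is stopped and the stop is recorded as exit. Later serious events in the 120 h window can then be missing from the Safety analysis.

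The size cannot be computed from the documents. The range of -1.5 to -7.5 points rests on assumed exit and event rates and on no early exits among controls; it halves if controls exit at half the Starling rate and vanishes if exits are equal. The documents do not support stating that exit is automatic, that the bias favours Starling, or that the formally tested endpoints are biased by this route.

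**What to change.** - In Protocol 8.7, 8.7.1 and, for subjects already randomized, 9.2, define two separate events: (a) device, algorithm or recording stopped; (b) consent for data collection withdrawn. The grounds for stopping are not touched.
- Subjects in (a) stay in the study and in the Safety set. Serious adverse events are collected over the existing 72 h + 48 h window. Event resolution, RRT, ventilation and vital status are collected to hospital discharge by chart review.
- In Protocol 12.2.1, replace study exit with the end of that window, except for screen failures and withdrawn consent.
- Reconcile that window with the 30-day summaries in SAP 9.2.2.1 and 10.1 and with the 72-hour limit for serious events in SAP 10.1. Reconcile exclusion criterion 26 with the ITT and Safety definitions, so that leaving the algorithm after randomization does not remove a patient from the Safety set.

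The cost is a protocol and SAP wording change and a little more chart review and data entry, mostly for inpatients; Table 1 already uses chart review for creatinine after 72 hours. The change improves the Safety-set results and makes an ITT analysis possible with complete data. It does not by itself alter the PP and mITT results.
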